7.1 Discontinuation of Study Intervention

It may be necessary for a participant to permanently discontinue study intervention. If study intervention is permanently discontinued, the participant will remain in the study to be evaluated for lipid profile. See the SoA in Section 1.3 for data to be collected at the time of discontinuation of study intervention and follow-up and for any further evaluations that need to be completed.

The following criteria should be considered for discontinuation:

- Protocol deviation
- Lost to follow-up
- AST or ALT level $> 3 \times \text{ULN}$ for 2 consecutive times
- CK $> 10 \times \text{ULN}$ for 2 consecutive times
- Pregnancy
- Termination of the study by the investigator or Sponsor
- Difficult to continue the study according to the judgment of the investigator
- Adverse event
- Withdrew informed consent

If a participant who does not meet enrollment criteria is inadvertently enrolled, that participant must be discontinued from study intervention and the Sponsor or designee, must be contacted. An exception may be granted in rare circumstances for which there is a compelling safety reason to allow the participant to continue. In these rare cases, the investigator must obtain documented approval from the Sponsor or designee, to allow the participant to continue in the study.

Participants who discontinue study intervention will not be replaced.

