8.3.4 Clinical Safety Laboratory Tests

See Section 10.2 for the list of clinical laboratory tests to be performed.

The investigator must review the laboratory report, document this review, and record any clinically significant changes occurring during the study as an AE. The laboratory reports must be filed with the source documents.

Abnormal laboratory findings associated with the underlying disease are not considered clinically significant unless judged by the investigator to be more severe than expected for the participant's condition.

All laboratory tests with values considered clinically significantly abnormal during participation in the study should be repeated until the values return to normal or baseline or are no longer considered clinically significant by the investigator or medical monitor. However, abnormal lab result will not be followed up after study completion.

If clinically significant values do not return to normal/baseline within a period of time judged reasonable by the investigator, the etiology should be identified, and the Sponsor or designee notified.

If laboratory values from non-protocol-specified laboratory tests performed at the site's local laboratory require a change in participant management or are considered clinically significant by the investigator (e.g., SAE or AE or dose modification), then the results must be recorded.

8.3.5 **Pregnancy Testing**

Women of childbearing potential (WOCBP) should only be included after a confirmed menstrual period and a negative highly sensitive urine or serum pregnancy test.

Additional pregnancy testing should be performed at each visit during the treatment period and as required locally.

Pregnancy testing will be performed whenever a menstrual cycle is missed or when pregnancy is otherwise suspected.

8.4 **Adverse Events, Serious Adverse Events, and Other Safety Reporting**

The definitions of AEs and SAEs can be found in Section 10.3. Treatment-emergent adverse events (TEAEs) are defined as AEs that first occurred or worsened in severity after the first administration of the study treatment during the treatment period.

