Adverse events will be reported by the participant (or, when appropriate, by a caregiver, surrogate, or the participant's legally authorized representative). The investigator who is a qualified physician, will assess events that meet the definition of an AE or SAE with respect to seriousness, severity and causality. The investigator and authorized study site staffs are responsible for detecting, documenting, and recording events that meet the definition of an AE or SAE and remain responsible for following up all AEs (see Section 10.3). For any guidance regarding AE/SAE reporting, the Investigator should contact the medical monitor.

The method of recording, evaluating, and assessing causality of AEs and SAEs and the procedures for completing and transmitting SAE reports are provided in Section 10.3.

8.4.1 **Time Period and Frequency for Collecting AE and SAE Information**

From the time of screening to the last visit, all AEs, SAEs, and other reportable safety events must be recorded and reported by the investigator to the Sponsor or designee within the time frames indicated in Table 8-1.

Additionally, any SAE brought to the attention of the investigator at any time outside the period specified in the previous paragraph must be reported immediately.

Table 8-1 Reporting Time Periods and Time Frames for Adverse Events, Serious Adverse Events, and other reportable safety events.

Type of Event	Reporting Time Period: Treatment Allocation Through End of Study	Time Frame to Report Event and Follow-up Information to Sponsor or designee
Adverse Event (AE)	Report all	Per study manual
Serious Adverse Event (SAE)	Report all	Within 24 hours of learning of event
Pregnancy/Lactation Exposure	Report all	Within 24 hours of learning of event

All AE/SAEs will be collected from the study participation until the last visit. However, if events are collected up to a period of 14 days after the intake of study treatment, it is recorded as AEs.

All SAEs will be recorded and reported to the Sponsor or designee immediately and under no circumstance should this exceed 24 hours of the investigator's awareness of the event, as indicated in Section 10.3. The investigator will submit any updated SAE data to the Sponsor or designee within 24 hours of their awareness of the updated information.

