10.3.1 Definition of AE

AE Definition

- An AE is any untoward medical occurrence in a clinical study participant administered a medicinal product and which does not necessarily have a causal relationship with that product.
- NOTE: An AE can therefore be any unfavorable and unintended sign (including an abnormal laboratory finding, for example), symptom, or disease (new or exacerbated) temporally associated with the use of study intervention/treatment, whether or not considered related to the study intervention/treatment by the investigator.
- AEs are defined as events occurring from screening to the last visit.
- TEAEs are defined as AEs that first occurred or worsened in severity after the first administration of the study treatment during the treatment period.

Events Meeting the AE Definition

- Any abnormal laboratory test results (hematology, clinical chemistry, or urinalysis) or other safety assessments (e.g., ECG, radiological scans, vital signs measurements), including those that worsen from baseline, considered clinically significant in the medical and scientific judgment of the investigator (ie, not related to progression of underlying disease).
- Exacerbation of a chronic or intermittent pre-existing condition including either an increase in frequency and/or severity of the condition.
- New condition detected or diagnosed after screening visit even though it may have been present before the start of the study.
- Signs, symptoms, or the clinical sequelae of a suspected intervention-intervention interaction.
- Signs, symptoms, or the clinical sequelae of a suspected overdose of either study intervention or a concomitant medication. Overdose per se will not be reported as an AE/SAE unless it is an intentional overdose taken with possible suicidal/self-harming intent. Such overdoses should be reported regardless of sequelae.
- Lack of efficacy or failure of expected pharmacological action per se will not be reported as an AE or SAE. Such instances will be captured in the efficacy assessments. However, the signs, symptoms, and/or clinical sequelae resulting from lack of efficacy will be reported as AE or SAE if they fulfill the definition of an AE or SAE.

Events NOT Meeting the AE Definition

- Any clinically significant abnormal laboratory findings or other abnormal safety assessments that are associated with the underlying disease, unless judged by the investigator to be more severe than expected for the participant's condition.

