16.2 Adverse Events

The definition of AEs in the study protocol is restricted to the treatment-emergent adverse events (TEAEs) occurring after the first treatment exposure, while for this study AEs were collected from screening.

A TEAE is defined as AEs that first occurred or worsened in severity on or after the first administration of the study treatment during the treatment period.

TEAEs at 6 weeks will include TEAEs with the start date prior to 6 week (< Day 43) after the first administration of the study treatment. Imputation rules of partial/missing start/stop date on the AEs will be applied according to Appendix 1. Except for imputation of partial dates, no imputation will be done for missing values for all safety analyses.

A treatment-emergent serious adverse event (TESAE) and a treatment-related adverse event (TRAE) is identified by the response of 'Yes' on the Seriousness and Causality, respectively, on the AE page of eCRF. A TEAE leading to the premature discontinuation of the study is one with the response of 'Drug Withdrawn' on 'Action Taken with Study Drug' on the AE page of eCRF.

The number and percentage of patients experiencing at least one of TEAEs, TESAEs, TRAEs, and TEAEs leading to the premature discontinuation of the study at 6 weeks and 12 weeks will be presented by treatment group and tested using Chi-square test or Fisher's exact test as appropriate. The difference in the percentages will be presented with its corresponding 95% CI and p-value.

In addition, the numbers and percentages of patients experiencing at least one of TEAEs will be summarized by SOC and PT according to the MedDRA dictionary for each treatment group.

Individual TESAEs and TEAEs leading to the premature discontinuation of the study will be also listed with details including patient number, institution name, treatment group, sex, age, reported term, SOC, PT, start and stop date, severity, seriousness with criteria, causality, action taken and outcome.

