17.1 APPENDIX 1. Partial Date Conventions

Imputed dates will NOT be presented in the listings.

ALGORITHM FOR TREATMENT EMERGENCE OF ADVERSE EVENTS:

START DATE	STOP DATE	ACTION
Known	Known	
 The start date of AE < the first date of study treatment, Non-TEAEs
	Partial	
 the start date of AE \geq the first date of study treatment, TEAEs
	Missing	
(For TEAE at 6 weeks, the start date of AE \geq the first date of study treatment and the start date of AE < the first date of study treatment + 6 weeks)

Partial	Known	
In case of missing or unknown month and day of the start date of AE,
 
 The year of the start date of AE < the year of the first date of study treatment, Non-TEAEs; The year of the start date of AE = the year of the first date of study treatment and the stop date of AE < the first date of study treatment, Non-TEAEs; The year of the start date of AE = the year of the first date of study treatment and the stop date of AE \geq the first date of study treatment, TEAEs; The year of the start date of AE > the year of the first date of study treatment, TEAEs; 
(For TEAEs at week 6, the year of the start date of AE > the year of the first date of study)

Document: Document path and title

Template No.: CCI

Reference: CCI

Effective Date: 15Oct2021

START DATE	STOP DATE	ACTION
		
treatment and the month and day of the first date of study treatment \geq 21st Nov)
 
In case of missing or unknown day of the start date of AE,
 
 • The year and month of the start date of AE < the year and month of the first date of study treatment, Non-TEAEs; • The year and month of the start date of AE = the year and month of the first date of study treatment and the stop date of AE < the first date of study treatment, Non-TEAEs; • The year and month of the start date of AE = the year and month of the first date of study treatment and the stop date of AE \geq the first date of study treatment, TEAEs; • The year and month of the start date of AE > the year and month of the first date of study treatment, TEAEs 
(For TEAEs at week 6, the year and month of start date \leq the year and month of the first date of study treatment + 6 weeks)

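### SAP Appendix 1 has no branch for worsening, so an AE that starts before first dose and becomes more severe on treatment meets the TEAE definition but is classified as not treatment-emergent

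*SAP*

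**What the plan says.** **Definition.** Protocol 8.4 and 10.3.1 define TEAEs as "AEs that first occurred or worsened in severity after the first administration of the study treatment during the treatment period". SAP 16.2 has the same two limbs and makes the first-dose date inclusive: "AEs that first occurred or worsened in severity on or after the first administration of the study treatment during the treatment period". An AE can thus qualify by first occurrence or by worsening.

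**Algorithm.** SAP Appendix 1 goes beyond imputing incomplete dates. Its first block covers AEs with a known start date, whether the stop date is known, partial or missing. There the rule is "The start date of AE < the first date of study treatment, Non-TEAEs", and an AE starting on or after first dose is a TEAE. For the 6-week count the start must also fall before first dose plus 6 weeks.

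**Collection.** Protocol 10.3.1 says "AEs are defined as events occurring from screening to the last visit", and SAP 16.2 confirms that AEs were collected from screening. Protocol 10.3.3 says that new or updated information goes into the originally submitted documents.

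**Use.** TEAEs, and dropout due to TEAEs, at 6 and 12 weeks are secondary endpoints. SAP 16.2 reports them with between-arm differences, confidence intervals and p-values.

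**The concern.** The definition and the rule that applies it disagree about one kind of event. A programmer working from SAP 16.2 would look for an increase in severity after first dose. One working from Appendix 1 would compare two dates and stop. For an AE present before dosing that worsens on drug, they would reach opposite answers.

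The classification carries through to other outputs. Serious TEAEs and TEAEs leading to discontinuation are subsets of TEAEs. An AE that was mild at screening, then became serious or led to drug withdrawal on treatment, would be absent from the summary tables (Tables 147 to 149) and from the individual listings (Tables 150 and 151). The trial is open-label, which is a further reason to fix the rule in advance.

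**Working it through.** The plan states no figure to reproduce. The check applies both rules to the same events. Day 1 is the first dose; SAP 7.1 has no Day 0, so Day -3 is three days before it.

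| Event | Definition (SAP 16.2) | Appendix 1, known start date |
|---|---|---|
| Onset Day 10, on drug | TEAE | TEAE |
| Onset Day -3, never worsens | not a TEAE | not a TEAE |
| Onset Day -3, worsens Day 20 on drug | TEAE | **not a TEAE** |
| Onset Day -3, worsens Day 50 on drug | TEAE | **not a TEAE** |

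**6-week cut.** First dose plus 6 weeks is Day 1 + 42 = Day 43, which agrees with the limit in SAP 16.2. The cut is written on the AE start date. A repaired rule must use the date of worsening: the Day 20 event then belongs in both the 6- and 12-week counts (20 < 43), and the Day 50 event only in the 12-week count (50 > 43).

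**Other branches.** None reads severity. When the start date is partial (same month or year as first dose) or missing, an AE whose stop date is on or after first dose is a TEAE. A poorly dated AE that spans first dose is therefore counted, while a fully dated one that worsened on drug is not.

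**Size.** The documents give no AE rates, so no count can be computed. Two bounds are available.
- Opportunity: the Schedule of Activities places screening from Day -7 to Day 1 and allows Visits 1 and 2 on the same day. Pre-dose time under observation is therefore between zero and about a week.
- Effect per patient: with 63 randomised per arm, one reclassified patient changes that arm's percentage by 1/63 = 1.6 points. In the any-TEAE row this happens only if the patient has no other TEAE.

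**End of the treatment period.** Appendix 1 also ignores the last-dose date. Protocol 7.1 says that after permanent discontinuation of drug "the participant will remain in the study to be evaluated for lipid profile", so off-drug AEs can arise. Take a last dose on Day 20 and onset on Day 25 or Day 40:
- treatment period ends at last dose: neither is a TEAE;
- it ends 14 days after last dose (20 + 14 = Day 34): Day 25 is, Day 40 is not;
- it runs to the last visit: both are, as in Appendix 1.

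Neither document says which is meant.

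**The case against.** **Worsening.** The best defence is that data entry may close the gap. Protocol 10.3.1 lists exacerbation of a pre-existing condition, including greater severity, as an AE in its own right, so a site could enter the worsening with its own onset date. SAP 16.2 states the definition in full and cites Appendix 1 only for partial or missing dates. Table 8-1 heads its reporting period as starting at treatment allocation, which would leave little pre-dose time.

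This shows that the gap may not bite, and it limits the size. It does not remove the inconsistency. No rule requires a new record for an AE already on file, and protocol 10.3.3 points towards updating the existing one. Appendix 1 also classifies fully dated events explicitly.

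**Stronger readings that a reader might infer.**
- *That Appendix 1 wrongly counts off-drug events.* AE collection stops at the last visit, which is an upper limit in practice, and the Schedule labels Visits 2 to 4 the intervention period. On that tenable reading Appendix 1 is right. The fault is an undefined term.
- *That it contradicts a 14-day window.* Protocol 8.4.1 says "However, if events are collected up to a period of 14 days after the intake of study treatment, it is recorded as AEs". That is a rule for recording AEs, and no TEAE definition refers to it.
- *That off-drug events dilute the difference between arms.* The analysis counts patients with at least one TEAE. A patient who stopped because of a TEAE is already counted, and extra events in the less well tolerated arm could widen the difference. The documents do not establish a direction.

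**Conclusion.** The point holds for worsening. Appendix 1 leaves out one of the two limbs of the TEAE definition, so an AE that starts before first dose and worsens on treatment can be missed in a secondary safety endpoint. This assumes that worsening is recorded by updating the existing AE; if sites always open a new record with a new start date, the gap closes.

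The effect is probably small because pre-dose observation is short, though the documents do not allow an estimate. SAP 8.2 draws inferential conclusions only from the primary endpoint, so the trial's main result is not affected. The end of the treatment period needs clarifying but is not a demonstrated error.

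**What to change.** Change the SAP only.

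1. In the Appendix 1 rows for AEs starting before first dose, add that an AE whose severity rises above its pre-dose level on or after first dose, within the treatment period, is a TEAE. Date it at the worsening, including for the 6-week cut. Alternatively, state that worsening is entered as a new record with its own start date, and confirm that the AE data were collected that way.
2. As a secondary clarification, state in SAP 16.2 when the treatment period ends for a patient who stops drug but stays in the study: last visit, last dose, or a stated time after last dose. Tabulate any later events separately as off-treatment.

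The cost is a few lines of SAP text and a small programming change. Severity and the last-dose date already feature in the planned outputs (SAP 16.2 and 16.1). If existing records hold only one severity per AE with no date of change, sites would have to be queried for the few AEs that began before first dose. No protocol amendment is needed.

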3.0 OBJECTIVES AND ENDPOINTS

Table 3-1 presents the objectives and corresponding endpoints of the study.

Table 3-1 Study objectives and endpoints

Objectives	Endpoints

Primary
 
 • To evaluate the effectiveness of early add-on of ezetimibe with atorvastatin in very high-risk patients. 	
 • Percentage change in LDL-C from baseline to week 6

Secondary
 
 • To evaluate the clinical effectiveness of early add-on of ezetimibe with atorvastatin in very high-risk patients. • To evaluate the safety of early add-on of ezetimibe with atorvastatin in very high-risk patients. 	
 • Proportion of patients achieving LDL-C goal of <55 mg/dL after 6 weeks and 12 weeks of treatment • Proportion of patients achieving LDL-C goal of <70 mg/dL after 6 weeks and 12 weeks of treatment • Percentage change in LDL-C from baseline to week 12 • Percentage change in HDL-C, non-HDL-C, triglycerides, and total cholesterol from baseline to week 6 and week 12 • Treatment-emergent adverse events (TEAEs) at 6 weeks and 12 weeks • Dropout rate due to TEAEs at 6 weeks and 12 weeks

Abbreviations: LDL-C=Low-density lipoprotein cholesterol; HDL-C= High-density lipoprotein cholesterol

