	Partial	Missing or unknown month and day of the stop date of AE will be replaced by 31st Dec. Missing or unknown day of the stop date of AE will be replaced by the last day of the month.

 Document: Document path and title

Template No.: CCI [REDACTED]

Reference: CCI [REDACTED]

Effective Date: 15Oct2021

START DATE	STOP DATE	ACTION
		
In case of missing or unknown month and day of the start date of AE,
 
 • The year of the start date of AE < the year of the first date of study treatment, Non-TEAEs; • The year of the start date of AE = the year of the first date of study treatment and the stop date < the first date of study treatment, Non-TEAEs; • The year of the start date of AE = the year of the first date of study treatment and the stop date \geq the first date of study treatment, TEAEs; • The year of the start date of AE > the year of the first date of study treatment, TEAEs 
(For TEAEs at 6 weeks, the year of the start date of AE > the year of the first date of study treatment and the month and day of the first date of study treatment \geq 21st Nov)
 
In case of missing or unknown day of the start date of AE,
 
 • The year and month of the start date of AE < the year and month of the first date of study treatment, Non-TEAEs; • The year and month of the start date of AE = the year and month of the first date of study treatment and the stop date < the first date of study treatment, Non-TEAEs;

 Document: Document path and title

Template No.: CCI

Reference: CCI

Effective Date: 15Oct2021

START DATE	STOP DATE	ACTION
		
 The year and month of the start date of AE = the year and month of the first date of study treatment and the stop date \geq the first date of study treatment, TEAEs The year and month of the start date of AE $>$ the year and month of the first date of study treatment, TEAEs (For TEAEs at 6 weeks, the year and month of start date \leq the year and month of the first date of study treatment + 6 weeks)

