	Missing	
In case of missing or unknown month and day of the start date of AE,
 
 The year of the start date of AE $<$ the year of the first date of study treatment, Non-TEAEs; the year of the start date of AE \geq the year of the first date of study treatment, TEAEs (For TEAEs at 6 weeks, the year of the start date of AE = the year of the first date of study or the year of the start date of AE $>$ the year of the first date of study treatment and the month and day of the first date of study treatment \geq 21st Nov) 
In case of missing or unknown day of the start date of AE,
 
 The year and month of the start date of AE $<$ the year and month of the first date of study treatment, Non-TEAEs;

Document: Document path and title

Template No.: CCI

Reference: CCI

Effective Date: 15Oct2021

START DATE	STOP DATE	ACTION
		
 The year and month of the start date of AE \geq the year and month of the first date of study treatment, TEAEs 
(For TEAEs at 6 weeks, the year and month of start date \leq the year and month of the first date of study treatment + 6 weeks)

Missing	Known	
 The stop date of AE $<$ the first date of study treatment, Non-TEAEs; The stop date of AE \geq the first date of study treatment, TEAEs and TEAEs at 6 weeks
	Partial	
Missing or unknown month and day of the stop date of AE will be replaced by 31st Dec. Missing or unknown day of the stop date of AE will be replaced by the last day of the month.
 
 The stop date of AE $<$ the first date of study treatment, Non-TEAEs; The stop date of AE \geq the first date of study treatment, TEAEs and TEAEs at 6 weeks
	Missing	TEAEs as well as TEAEs at 6 weeks

 Document: Document path and title

Template No.: CCI [REDACTED]

Reference: CCI [REDACTED]

Effective Date: 15Oct2021

ALGORITHM FOR PRIOR/ CONCOMITANT MEDICATIONS/ PROCEDURES:

START DATE	STOP DATE	ACTION
Will not imputed	Known	If the stop date of medications/procedures < the first date of study treatment, assign as prior; If the stop date of medications/procedures \geq the first date of study treatment or if ongoing is checked, assign as concomitant

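### For adverse events with only the start year known, two of the three 6-week TEAE rules in SAP Appendix 1 omit same-year onsets, so a recorded stop date drops an event that a blank one would keep

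*SAP*

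**What the plan says.** Protocol section 3.0 lists as a secondary endpoint "Treatment-emergent adverse events (TEAEs) at 6 weeks and 12 weeks". SAP section 16.2 defines the earlier time point: "TEAEs at 6 weeks will include TEAEs with the start date prior to 6 week (< Day 43" of dosing), and refers partial dates to Appendix 1 (SAP 17.1).

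For a start date with month and day both unknown, Appendix 1 has three rows.

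- **Known stop date.** A same-year start with a stop on or after first dose is a TEAE. The 6-week bracket begins "For TEAEs at week 6, the year of the start date of AE > the year of the first date of study" and adds that first dose must fall on or after 21 November.
- **Partial stop date.** The stop is first completed to its latest possible date: "Missing or unknown month and day of the stop date of AE will be replaced by 31st Dec", or by the month's last day if only the day is unknown. The TEAE bullets then work as above, for example "The year of the start date of AE = the year of the first date of study treatment and the stop date" on or after first dose. The 6-week bracket is the same: "For TEAEs at 6 weeks, the year of the start date of AE > the year of the first date of study treatment", with the 21 November condition.
- **Missing stop date.** The 6-week bracket opens with a further alternative, "For TEAEs at 6 weeks, the year of the start date of AE = the year of the first date of study", before giving the later-year and 21 November condition.

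If only the start day is unknown, every row uses a month comparison, for example "For TEAEs at week 6, the year and month of start date" no later than the month of first dose plus 6 weeks. If the start is wholly missing and the stop is on or after first dose or also missing, the event counts as a TEAE and as a 6-week TEAE.

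**The concern.** The same-year alternative stands in one of three parallel rows. Almost every onset in the first six weeks falls in the calendar year of first dose, so the two rows without it omit the usual case and keep only the year-end exception.

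The result runs against the information available. A recorded stop date can only narrow the possible onset, yet recording one takes the event out of the 6-week count. Knowing less, by losing either the stop date or the start year, puts it back.

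The rule feeds the whole 6-week adverse event summary in Table 147 (any TEAE, serious, treatment-related, and leading to discontinuation), each line with a difference, a confidence interval and a p-value. An affected event would appear in the 12-week table but not the 6-week table, and would look as if it had arisen after Week 6.

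**Working it through.** **Inputs.** A 6-week TEAE starts before Day 43, that is, before first dose + 42 days (SAP 16.2; Day 1 is the first dose, SAP 7.1). The row conditions and the 21 November cut-off are from SAP 17.1. The planned number is 63 per arm (SAP 4.2).

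**Step 1: the plan's own cut-off.** A next-year onset can be before Day 43 only if 1 January is. From 21 November to 1 January is 9 + 31 + 1 = 41 days, so 1 January is Day 42 and qualifies. With first dose on 20 November it is Day 43 and does not. The 21 November date is therefore correct; the fault lies elsewhere in the bracket.

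**Step 2: apply the rows literally.** With first dose on 1 March 2023, Day 43 is 12 April 2023.

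| Recorded start | Recorded stop | TEAE | 6-week TEAE |
|---|---|---|---|
| 2023 only | 20 Mar 2023 | yes | no |
| 2023 only | Mar 2023 (set to 31 Mar) | yes | no |
| 2023 only | missing | yes | yes |
| missing | 20 Mar 2023 | yes | yes |
| missing | 20 May 2023 | yes | yes |
| Mar 2023, day missing | 20 Mar 2023 | yes | yes |

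In the first two lines the event ended before 12 April, so it cannot have begun on or after Day 43. It is still left out of the 6-week count.

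**Step 3: where the fault stops.** Take first dose on 1 December 2023, start 2024 only, stop 5 January 2024 (Day 36). The start year is later and first dose is after 21 November, so the event is counted, and correctly. Later-year starts are not affected, and neither are starts lacking only the day.

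**Step 4: how much of the branch is affected.** As an illustration, assume first doses spread evenly over a 365-day year and onsets spread evenly over Days 1 to 42. There are 365 × 42 = 15,330 combinations. Those crossing into the next year number 1 + 2 + … + 41 = 861 (first doses 21 November to 31 December). Same-year share = 1 − 861/15,330 = 94.4%. Under this assumption, that share of true 6-week events with a year-only start and a recorded stop fails the literal rule. With the stop missing, none fails. This is a share within a rare branch, not a rate for the trial.

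**Step 5: effect on the endpoint.** The rate counts patients with at least one event. With 63 patients in an arm's safety set, one reclassified patient moves it by 1/63 = 1.6 points, two by 3.2 and three by 4.8. Zero to three patients is an assumed range.

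**The case against.** The best counter-argument concerns the bracket. In the known-stop and partial-stop rows it follows a bullet about later-year starts, and it may qualify only that bullet. In the missing-stop row it follows a merged bullet covering same-year and later-year starts, which would explain why it names both. On that reading nothing is excluded; the two rows are silent on same-year events. This is possible but less natural. The brackets for starts lacking only the day occupy the same position, and their month condition plainly covers the earlier bullets as well. Silence would also leave these events without a 6-week rule, and the same edit would be needed.

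A reader might infer more than the text supports in three ways.

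- That any partly dated event with a stop date is lost. Only starts with both month and day unknown are affected.
- That the omitted events are proven to have begun within six weeks of dosing. A stop before Day 43 proves onset before Day 43. That onset followed first dose is normally the SAP's convention, since adverse events are collected from screening. Exceptions exist: with first dose on 1 January, a same-year start and a stop on 20 January, the dates prove both, and the event is still omitted.
- That the rule fails for every event stopping before Day 43. The December example in the working shows that it does not.

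The case for low impact stands. SAP 8.2 reserves inferential conclusions for the primary endpoint, so the 6-week p-values carry no formal weight. In a study of about 13 weeks with adverse event review at each treatment visit, an onset month that stays unknown should be rare.

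**Conclusion.** The inconsistency is real, and it is a minor drafting fault. Read literally, the known-stop and partial-stop rows leave out of the 6-week count same-year, year-only events that the SAP itself classes as TEAEs. Where the stop is before Day 43, the omission contradicts the definition in SAP 16.2. Where the stop is on or after Day 43, onset within six weeks is possible but not shown; the fault there is different treatment of the same event from the missing-stop row.

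The largest effect is 1.6 points on one arm's 6-week rate per affected patient, and none if that patient has another 6-week TEAE. This assumes the planned 63 per arm all enter the safety set. The number of affected events is not in the documents and is assumed to be few. The 12-week and overall TEAE counts and the primary endpoint do not change.

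**What to change.** In the year-only part of the known-stop and partial-stop rows, replace the 6-week bracket with the missing-stop condition, applied to events already classed as TEAEs: the start year equals the year of first dose, or the start year is later and first dose is on or after 21 November. Refer explicitly to the first date of study treatment, because the same-year clause in the missing-stop row leaves out the word treatment.

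No extra sentence about stop dates is needed. With the clause added, every TEAE stopping before Day 43 is counted:

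- a same-year start, by the new clause;
- a later-year start, because such a stop forces a first dose on or after 21 November;
- a start lacking only the day, because its month cannot be later than the stop month;
- a missing start, because it is always counted.

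The price is some overcounting: a same-year, year-only event that truly began after Week 6 will enter the 6-week count. The missing-stop row already accepts this, so the three rows would follow one inclusive convention. The cost is two bracket edits and the matching code, with no new data.
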